#### 7.2.9 Subject Care Implications

The overall safety experience with nivolumab is based on experience in approximately 1500 subjects as either a monotherapy or in combination with other therapeutics. In general for monotherapy, the safety profile is similar across tumor types. The one exception is pulmonary inflammation AEs which may be numerically greater in subjects with NSCLC possibly because in some cases it can be difficult to distinguish between nivolumab-related and unrelated causes of pulmonary symptoms and radiographic changes. The most frequently reported treatment related AE is fatigue which is almost always low grade.

Most related AEs are thought to be due to the effects of inflammatory cells on specific tissues. A variety of PTs have been used to describe similar kinds of organ-related AEs with the result being that AE frequency tables organized by PTs can lead to underestimation of the frequency of similar kinds of organ-related AEs. To address this issue, select AE categories were created. Select AE categories group together the most common and impactful PTs by organ category. These categories include the following: pulmonary, gastrointestinal, hepatic, dermatologic, endocrine, and renal AEs. It is also useful to consider the management of nivolumab-related AEs by organ category as the diagnostic workup often requires excluding other potential diagnoses and when appropriate instituting specific management principles as outlined in this protocol and Appendix 2.

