#### 12.4.3 Safety Analyses

Safety analysis will be performed in all treated subjects. Descriptive statistics of safety will be presented using National Cancer Institute (NCI) Common Terminology Criteria for Adverse Events (CTCAE) version 4.0. All on-study AEs, drug-related AEs, SAEs and drug-related SAEs, AEs and drug-related AEs leading to drug discontinuation will be tabulated using worst grade per NCI CTCAE v 4.0 criteria by system organ class and preferred term, based on MedDRA terminology. On-study lab parameters including hematology, coagulation, chemistry, liver function and renal function will be summarized using worst grade per NCI CTCAE v 4.0 criteria.

Frequency, management and resolution of IMAEs will be analyzed. A tabular summary of the incidence of overall IMAEs (by preferred term) and serious IMAEs will be performed. A descriptive analysis of IMAEs including time-to-onset, severity, duration, action taken with the study drug, dosing delays of the study drug, corticosteroid details, re-challenge information and outcome of the AE will be individually characterized by IMAE category ([Section 6.6.1](#)).

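### Immune-mediated AE incidence is planned by preferred term only; add subject-level incidence by the Table 2 categories, because the category rate cannot be recovered from preferred-term rows

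*Combined protocol and SAP*

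**What the plan says.** Section 12.4.3 (Safety Analyses) plans these summaries, all in treated subjects:

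- General AE tables, which "will be tabulated using worst grade per NCI CTCAE v 4.0 criteria by system organ class and preferred term, based on MedDRA terminology".
- A worst-grade summary of laboratory parameters, including liver and renal function.
- For immune-mediated AEs (IMAEs), a general statement, "Frequency, management and resolution of IMAEs will be analyzed", followed by the specific table: "A tabular summary of the incidence of overall IMAEs (by preferred term) and serious IMAEs will be performed".
- A descriptive account by category, covering onset, severity, duration and handling of study drug, in which "corticosteroid details, re-challenge information and outcome of the AE will be individually characterized by IMAE category".

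Section 6.6.1 defines the IMAE categories, and Table 2 assigns PTs to each. Outside the endocrine group, an event counts as an IMAE only if it was treated with immunosuppressive medication.

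Section 7.2.9, in the nivolumab drug information, says that "AE frequency tables organized by PTs can lead to underestimation of the frequency of similar kinds of organ-related AEs". It continues: "To address this issue, select AE categories were created". It explains that "Select AE categories group together the most common and impactful PTs by organ category".

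**The concern.** The one IMAE incidence table whose level is stated is set at the level that Section 7.2.9 describes as open to underestimation. The grouping that would answer the clinical question, how many treated subjects had hepatic or bowel immune toxicity, already exists in Table 2. Section 12.4.3 uses it to describe events but does not name it as a level for incidence.

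Safety and tolerability is the first secondary objective (Section 1.2.1), and Section 2.4 presents immune-related toxicity as the defining feature of the combination's safety profile. With at most 56 treated subjects, a handful of events split over several rows can make an organ toxicity look rarer than it is. A reader who adds the rows to compensate can overshoot, because one subject may appear in more than one row.

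**Working it through.** **Denominator.** The documents state no IMAE incidence, so the only plan figure to reproduce is the number treated. Section 12.2 gives a two-stage design: 20 subjects, stop if 1 or fewer respond, otherwise 56 in total, with the regimen rejected at 4 or fewer responses. By exact binomial:

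- Early stopping at p = 0.05: 0.95^20 + 20 × 0.05 × 0.95^19 = 0.7358 (stated 0.736).
- Expected size: 20 + (1 − 0.7358) × 36 = 29.51 (stated 29.51).
- Type I error 0.0967 and type II error 1 − 0.8010 = 0.1990 (stated 0.097 and 0.199).

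The denominator is therefore 56, or 20 if the trial stops after stage 1. One subject is 1/56 = 1.8 or 1/20 = 5.0 percentage points.

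**Which categories are exposed.** PTs per category in Table 2:

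- Hepatitis 8.
- Diarrhea/colitis 3.
- Nephritis and renal dysfunction 3.
- Pneumonitis 2.
- Diabetes mellitus 2.
- Hypothyroidism/thyroiditis 4 listed, 2 after the acute and autoimmune thyroiditis terms are merged for frequency, as Table 2 directs.
- Adrenal insufficiency, hyperthyroidism and hypophysitis 1 each. Here the PT row is the category rate, and the point does not arise.

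**What PT rows determine.** Let n1, ..., nk be the numbers of subjects in the k PT rows of one category, out of N treated. The number with at least one event in the category satisfies

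max(n1, ..., nk) ≤ affected subjects ≤ min(N, n1 + ... + nk).

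The lower bound holds under full overlap and the upper bound under none. The overlap is not in the table.

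**Diarrhea/colitis, assumed counts, N = 56.** Diarrhea 4, colitis 3, enterocolitis 2:

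- Rows: 4/56 = 7.1%, 3/56 = 5.4%, 2/56 = 3.6%.
- Full overlap: 4/56 = 7.1% (exact 95% CI 2.0 to 17.3).
- No overlap: (4 + 3 + 2)/56 = 9/56 = 16.1% (exact 95% CI 7.6 to 28.3).

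The same three rows fit every category count from 4 to 9.

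**Hepatitis, outer limit, assumed counts.** If 11 of 56 subjects (19.6%) were affected, each coded to one PT and spread evenly over 8 PTs, the largest row would be ceil(11/8) = 2, or 2/56 = 3.6%. With full overlap it would be 11/56 = 19.6%. The even split is an extreme: AST and ALT rises in the same subject would narrow the gap. Summing can err the other way: 11 subjects each with both AST and ALT increased give 22 row entries for 11 people.

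**The case against.** The strongest reply is that category incidence is nearly there already. Section 12.4.3 says IMAE frequency will be analysed, describes severity by category, and fixes the population as all treated subjects, while Table 2 supplies the mapping. A severity summary by category would normally show how many subjects were affected. That is fair, and it is why the remedy is cheap. But the general sentence on frequency names no level, the sentence that follows names PT, and no rule for counting a subject once per category is given.

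Other mitigating text also stands. The general AE tables have system organ class rows. Liver and renal laboratory values are summarised by worst grade, which matters for hepatitis because 4 of its 8 PTs are laboratory terms. Neither is incidence by Table 2 category, and the documents do not show how system organ class maps to those categories.

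Three stronger readings are tempting, and the documents do not support them:

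- That the planned tables will understate every organ toxicity. Section 7.2.9 says only that PT tables can do so, and three Table 2 categories have a single PT.
- That toxicity managed without immunosuppression appears in PT rows alone. It also contributes to the system organ class rows and, for liver and renal values, the laboratory summaries. Endocrine events count as IMAEs whatever the treatment.
- That leaving out the select AE categories contradicts the plan. They are described in a drug-information section, their PT lists are not given, and they are a different grouping from the IMAE categories that Section 12.4.3 does use.

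**Conclusion.** The point holds as a weakness in a secondary safety analysis. Section 12.4.3 specifies IMAE incidence at a level that the protocol itself says can mislead, although a better level is already defined in Table 2. For the six categories that still have more than one PT after the thyroiditis merge, the proportion of subjects affected cannot be recovered from the planned rows, whether by taking the largest or by adding them up.

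The size depends on overlap between PTs, which the documents do not give. In the worked example the rate is uncertain between 7.1% and 16.1%; the event counts are assumptions, so this shows what is possible and does not estimate the error. The sample size, the primary test and data collection are not affected.

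**What to change.** In Section 12.4.3, replace the PT-level IMAE incidence table with incidence by IMAE category (Table 2), with PTs nested below. Report the number and percentage of all treated subjects with at least one event, each subject counted once per category at worst grade, for any-grade, Grade 3 or higher, and serious events. The last also gives the serious IMAE summary the level it now lacks. Exact 95% CIs are optional.

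Because non-endocrine IMAEs require immunosuppressive treatment, the same Table 2 groupings can also be applied to all-cause and drug-related AEs regardless of that treatment. This needs no PT lists beyond those in Table 2. Rash is named in the Section 6.6.1 definition, but no row for it is visible in the text available for this review. It may have been lost when the document was read, so the sponsor need only check that its own copy has one.

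The cost is a change of wording and one or two extra tables from AE data already collected. Organ-level rates may look less favourable than the PT rows. Setting the grouping now avoids choosing it after the data are seen.

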**APPENDIX 1****ECOG PERFORMANCE STATUS**

ECOG PERFORMANCE STATUS a	
0	Fully active, able to carry on all pre-disease performance without restriction
1	Restricted in physically strenuous activity but ambulatory and able to carry out work of a light or sedentary nature, e.g., light house work, office work
2	Ambulatory and capable of all self-care but unable to carry out any work activities. Up and about more than 50% of waking hours
3	Capable of only limited self-care, confined to bed or chair more than 50% of waking hours
4	Completely disabled. Cannot carry on any self-care. Totally confined to bed or chair
5	Dead

a Oken MM, Creech RH, Tormey DC, Horton J, Davis TE, McFadden ET, and Carbone PP. Toxicity and Response Criteria of the Eastern Cooperative Oncology Group. Am J Clin Oncol 1982; 5: 649-655.

## **APPENDIX 2      MANAGEMENT ALGORITHMS FOR IMMUNO-ONCOLOGY AGENTS**

These general guidelines constitute guidance to the Investigator and may be supplemented by discussions with the IND Sponsor. The guidance applies to all immuno-oncology agents and regimens.

A general principle is that differential diagnoses should be diligently evaluated according to standard medical practice. Non inflammatory etiologies should be considered and appropriately treated.

[figure not shown]
Corticosteroids are a primary therapy for immuno-oncology drug-related adverse events. The oral equivalent of the recommended IV doses may be considered for ambulatory patients with low-grade toxicity. The lower bioavailability of oral corticosteroids should be taken into account when switching to the equivalent dose of oral corticosteroids.

Consultation with a medical or surgical specialist, especially prior to an invasive diagnostic or therapeutic procedure, is recommended.

The frequency and severity of the related adverse events covered by these algorithms will depend on the immuno-oncology agent or regimen being used.

# GI Adverse Event Management Algorithm

Rule out non-inflammatory causes. If non-inflammatory cause is identified, treat accordingly and continue I-O therapy. Opiates/narcotics may mask symptoms of perforation. Infliximab should not be used in cases of perforation or sepsis.

[figure not shown]

Patients on IV steroids may be switched to an equivalent dose of oral corticosteroids (e.g. prednisone) at start of tapering or earlier, once sustained clinical improvement is observed. Lower bioavailability of oral corticosteroids should be taken into account when switching to the equivalent dose of oral corticosteroids.

Updated 05-Jul-2016

# Pulmonary Adverse Event Management Algorithm

Rule out non-inflammatory causes. If non-inflammatory cause, treat accordingly and continue I-O therapy. Evaluate with imaging and pulmonary consultation.

[figure not shown]

Patients on IV steroids may be switched to an equivalent dose of oral corticosteroids (e.g. prednisone) at start of tapering or earlier, once sustained clinical improvement is observed. Lower bioavailability of oral corticosteroids should be taken into account when switching to the equivalent dose of oral corticosteroids.

Updated 05-Jul-2016

# Renal Adverse Event Management Algorithm

Rule out non-inflammatory causes. If non-inflammatory cause, treat accordingly and continue I-O therapy

[figure not shown]

Patients on IV steroids may be switched to an equivalent dose of oral corticosteroids (e.g. prednisone) at start of tapering or earlier, once sustained clinical improvement is observed. Lower bioavailability of oral corticosteroids should be taken into account when switching to the equivalent dose of oral corticosteroids.

Updated 05-Jul-2016

# Endocrinopathy Management Algorithm

Rule out non-inflammatory causes. If non-inflammatory cause, treat accordingly and continue I-O therapy. Consider visual field testing, endocrinology consultation, and imaging.

[figure not shown]

Patients on IV steroids may be switched to an equivalent dose of oral corticosteroids (e.g. prednisone) at start of tapering or earlier, once sustained clinical improvement is observed. Lower bioavailability of oral corticosteroids should be taken into account when switching to the equivalent dose of oral corticosteroids.

Updated 05-Jul-2016

# Hepatic Adverse Event Management Algorithm

Rule out non-inflammatory causes. If non-inflammatory cause, treat accordingly and continue I-O therapy. Consider imaging for obstruction.

Patients on IV steroids may be switched to an equivalent dose of oral corticosteroids (e.g. prednisone) at start of tapering or earlier, once sustained clinical improvement is observed. Lower bioavailability of oral corticosteroids should be taken into account when switching to the equivalent dose of oral corticosteroids.

[figure not shown]
\*I-O therapy may be delayed rather than discontinued if AST/ALT ≤ 8 x ULN or T.bili ≤ 5 x ULN.

\*\*The recommended starting dose for grade 4 hepatitis is 2 mg/kg/day methylprednisolone IV.

Updated 05-Jul-2016

# Skin Adverse Event Management Algorithm

Rule out non-inflammatory causes. If non-inflammatory cause, treat accordingly and continue I-O therapy.

Patients on IV steroids may be switched to an equivalent dose of oral corticosteroids (e.g. prednisone) at start of tapering or earlier, once sustained clinical improvement is observed. Lower bioavailability of oral corticosteroids should be taken into account when switching to the equivalent dose of oral corticosteroids.

\*Refer to NCI CTCAE v4 for term-specific grading criteria.

^If SJS/TEN is suspected, withhold I-O therapy and refer patient for specialized care for assessment and treatment. If SJS or TEN is diagnosed, permanently discontinue I-O therapy.

Updated 05-Jul-2016
